## **7.0 ADVERSE EVENTS**

## 7.1 Adverse Event Monitoring

Adverse event data collection and reporting, which are required as part of every clinical trial, are done to ensure the safety of subjects enrolled in the studies as well as those who will enroll in future studies. Adverse events are reported in a routine manner at scheduled times during a trial. Additionally, certain adverse events must be reported in an expedited manner to allow for optimal monitoring of subject safety and care.

All subjects experiencing an adverse event, regardless of its relationship to study therapy, will be monitored until:

- the adverse event resolves or the symptoms or signs that constitute the adverse event return to baseline or is stable in the opinion of the investigator;
- there is a satisfactory explanation other than the study therapy for the changes observed; or
- death.

### Definitions

**7.1.1** An adverse event is defined as any untoward or unfavorable medical occurrence in a human research study participant, including any abnormal sign (for example, abnormal physical exam, imaging finding or clinically significant laboratory finding), symptom, clinical event, or disease, temporarily associated with the subject's participation in the research, whether or not it is considered related to the subject's participation in the research.

Adverse events encompass clinical, physical and psychological harms. Adverse events occur most commonly in the context of biomedical research, although on occasion, they can occur in the context of social and behavioral research. Adverse events may be expected or unexpected.

### Acute Adverse Events

Iodine contrast is known to only have immediate side effects within the first 30 minutes of contrast injection. All subjects experiencing an adverse event will be monitored in Breast Imaging center for the first 30 minutes:

- Type and severity of contrast reaction or extravasation will be recorded.
- We will monitor the patient until the adverse event resolves or the symptoms or signs that constitute the adverse event return to baseline;
- Extravasation will be managed according to the Department of Radiology Standard operating procedures.

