### 3.2 Exclusion Criteria

- 3.2.1 History of ipsilateral mastectomy.
- 3.2.2 Women who already started neoadjuvant chemotherapy or endocrine therapy.
- 3.2.3 Woman who may be pregnant.
- 3.2.4 Prior history of anaphylactic or anaphylactoid reaction to any contrast.
- 3.2.5 Prior allergy to iodine or iodinated contrast.

Imaging Services will practice safe contrast administration through the evaluation of the patients' history via the electronic medical record and/or patient questionnaire.

Individualized, patient centric protocol planning, medication review, and contrast dosage will be utilized to reduce adverse events. Renal function testing is not routinely required for every patient receiving contrast. Creatinine and Estimated Glomerular Filtration Rate (eGFR) testing will be performed on patients at risk for contrast induced nephrotoxicity (CIN). Patients with reduced eGFR may be given intravenous (IV) iodinated contrast safely in many circumstances. Clinically significant nephrotoxicity after iodinated contrast media administration is highly unusual in patients with normal or mildly reduced renal function **GFR is tested in patients with a risk factor for decreased renal function.** Patients with one or more of the following conditions are considered to be at high risk for contrast induced nephropathy (CIN). These patients will be required to have renal function testing (eGFR) within 30 days before receiving intravenous iodinated contrast.

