##### 3.2.6

Eligible patients will be imaged at baseline (before initiation of neoadjuvant chemotherapy or endocrine therapy), early (2-4 cycles of neoadjuvant therapy) and late (after completion of neoadjuvant chemotherapy or endocrine therapy) timepoints with mammography. CEDM will be done within 2 weeks of the specified timepoint. Three dimensional orthogonal measurements will be obtained in all timepoints. Additional sites of disease in the ipsilateral or contralateral breast identified by CEDM will be recorded and reported. ACR BI-RADS MRI lexicon will be used for reporting.

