##### 4.1.1

The risks of CEDM include the risks of contrast administration including allergic reactions and renal function abnormalities. Just as with CT, patients will be screened for allergy history and possible renal function abnormalities. Allergic or physiologic reaction are reported to occur in less than 1% of patients when using low osmolar contrast agents although this increases in patients with prior reactions (11,12). Severe acute reactions occur in 4/10,000 (0.04%) of patients (13). Any contrast reaction will be handled in accordance with the Radiology Department's Contrast-Reaction Guidelines  
[https://hs.swmed.edu/communities\\_collaboration/radpoint/clinicaloperations/Practice%20Guidelines%20%20Procedures/Contrast%20Reactions%20-](https://hs.swmed.edu/communities_collaboration/radpoint/clinicaloperations/Practice%20Guidelines%20%20Procedures/Contrast%20Reactions%20-)

%20Pocket%20Guide.pdf#search=contrast%20reaction)Concomitant Medications/Treatments

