#### **4.3 Duration of Follow Up**

Adverse reactions to contrast will be monitored according to institutional guidelines. Patients will be observed for at least 30 minutes after contrast administration for any immediate side effects of contrast. Only contrast-specific side effects will be recorded, including moderate to severe allergic reactions to contrast, laryngospasm, angioedema, hypotension, bradycardia, diffuse hives.

Overall study duration is expected to be approximately 4-6 months from initiation of neoadjuvant therapy until final surgery in which negative margins are achieved.

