**5.3 Follow-up Procedures**

Patients' medical records will be followed 30 days after completion of definitive surgery to collect final pathology outcomes, or if they develop progressive disease.

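### The 30-minute statement in section 7.1 and the recording limit in section 4.3 conflict with the reporting duties in section 7.2 (minor)

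*Combined protocol and SAP*

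**What the plan says.** Two sentences set narrow rules.

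- Section 7.1, Acute Adverse Events, on timing: "Iodine contrast is known to only have immediate side effects within the first 30 minutes of contrast injection".
- Section 4.3, on scope: "Only contrast-specific side effects will be recorded". An open list of examples follows. It names allergic reactions only from moderate severity upward, and it names no renal event. The same section says: "Adverse reactions to contrast will be monitored according to institutional guidelines".

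Other sections are wider.

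- Section 4.1.1: "The risks of CEDM include the risks of contrast administration including allergic reactions and renal function abnormalities".
- Section 3.2 lists conditions that put a patient at high risk of contrast-induced nephropathy and adds: "These patients will be required to have renal function testing (eGFR) within 30 days before receiving intravenous iodinated contrast". Appendix A, item 3, repeats the rule.
- Section 7.2, note to Step 3, covers every event in the 30 minutes after a dose, plus any later event attributed to the agent as possible, probable or definite.
- Section 7.2, on the data safety monitoring committee (DSMC), requires all serious adverse events (SAEs) in a protocol-specified monitoring period to be submitted within 5 business days.
- Section 7.2, on events that do not qualify as unanticipated problems involving risks to subjects or others (UPIRSOs), requires them to be tracked, summarized and sent to the IRB at continuing review.
- Section 7.1 and its definitions apply to adverse events and SAEs whether or not they are related to the research.
- Section 6.2 asks for reactions to be recorded and graded with no lower limit on severity.

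**The concern.** A coordinator who works from section 4.3 is told not to record events that section 7.2 requires to be submitted or tracked. Reports to the DSMC and the IRB can contain only what was recorded.

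The timing sentence raises a second problem. After 30 minutes, the duty in the section 7.2 note depends on someone attributing the event to the agent. A flat statement that contrast has no later effects weighs against that attribution, and the renal risk named elsewhere is the obvious case. At stake are the completeness of safety recording and any statement about tolerability at the end of the study. The accuracy results are not at stake.

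**Working it through.** The plan gives no figure to reproduce, and the point depends on no sample size or event count. The check is a comparison of texts.

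1. **Timing against the late-event rule.** The section 7.2 note defines two classes: (a) all events within 30 minutes, and (b) later events attributed to the agent. If the section 7.1 sentence were true, class (b) would always be empty and the rule would have no purpose. This is a direct conflict.

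2. **Timing against renal risk.** Sections 3.2 and 4.1.1 and Appendix A treat renal harm as a risk of contrast and screen for it with eGFR, a laboratory value that bedside observation does not provide. The documents do not say when such harm appears, so this is a tension and not a proven contradiction.

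3. **Scope against reporting duties.** Take the example in section 7.1 of an unrelated car accident with an inpatient admission of at least 24 hours. Section 7.1 calls it an SAE. Section 7.2 requires its submission to the DSMC if it falls in the monitoring period. Section 4.3 would leave it unrecorded. A non-serious unrelated event meets the same obstacle under the rule for non-UPIRSO events.

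4. **Scope against definitions.** The rule in section 7.1 to monitor until resolution, and its definitions of adverse event and SAE, are not limited by cause. They do not themselves say what is recorded, so they support step 3 but would not establish it alone.

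5. **Severity.** Section 6.2 covers reactions of any grade. The allergic reactions listed in section 4.3 start at moderate. The list is open, so this is a mismatch of wording.

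6. **Window.** No section labels the monitoring period on which the DSMC rule relies.
 - Narrowest reading: the 30 minutes after each of three planned contrast-enhanced mammograms (CEDMs; baseline, mid-therapy, pre-operative), so 3 × 30 = 90 minutes per patient, plus later attributed events.
 - Wide reading, as an assumption: the roughly 4–6 months that section 4.3 gives from start of therapy to final surgery.
 - Section 5.3 does not settle it: "medical records will be followed 30 days after completion of definitive surgery to collect final pathology outcomes" gives a chart review for pathology and progression, not a safety window.
 - Even on the narrowest reading, section 7.2 takes in all events in the 30 minutes and section 4.3 only the contrast-specific ones. The scope conflict shrinks but remains.

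**The case against.** The strongest reply is that these are loose sentences in a protocol that handles safety adequately elsewhere. The timing sentence stands under a heading about acute events, and its bullets concern contrast reactions and extravasation. Renal risk is managed separately, by eGFR before contrast in high-risk patients, a stop rule, and a technologist's review of every patient's records for renal results. History is repeated at all three timepoints. Section 7.2 expressly requires SAE submission, and section 9.4 provides quarterly DSMC review of adverse events. The institutional contrast guidelines and the DSMC plan are not in the documents, so a failure in practice cannot be shown.

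Much of this stands and keeps the point minor. It does not reconcile the sentences: the heading leaves the 30-minute claim unqualified, screening before contrast does not record what follows, and the DSMC cannot review an unrecorded event.

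A reader might infer more than the documents support:

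- *That section 4.3 excludes renal events.* It does not. A renal event caused by contrast is contrast-specific, and the list is open.
- *That renal testing after contrast is a required but missing element.* The documents give no renal event rate and no share of high-risk patients, no objective concerns safety, and section 3.2 states: "Clinically significant nephrotoxicity after iodinated contrast media administration is highly unusual in patients with normal or mildly reduced renal function". If the 30-day rule is applied before each CEDM, a patient at high risk throughout has a later required eGFR after at most 3 − 1 = 2 of 3 CEDMs. One cannot say that all other patients have none, because a patient can become high-risk between scans.
- *That the SAE definition also depends on an undefined period.* The phrase there belongs to a generic illustration. Only the DSMC reporting rule uses it operatively.
- *That SAEs will be missed.* Staff may follow section 7.2 and not section 4.3. The documents show conflicting instructions, not lost events.

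**Conclusion.** Minor, and wrong as written. Two conflicts are established from the text alone: the 30-minute statement against the late-event rule in section 7.2, and the recording limit in section 4.3 against the SAE and non-UPIRSO rules in section 7.2. The tension with renal risk and the severity mismatch with section 6.2 are secondary.

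The effect on the AUC, sensitivity, specificity and size-correlation results is nil. Section 2 has no safety objective or endpoint, and section 8 has no safety analysis. The effect on safety capture cannot be quantified. The conclusion assumes only that the sections are read as they stand. The unseen institutional documents could soften the practical effect but would not make the protocol's sentences agree.

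**What to change.** 1. In section 7.1, Acute Adverse Events, limit the 30-minute sentence to acute hypersensitivity or physiologic reactions and extravasation.
2. In section 4.3, replace the recording limit with one rule consistent with sections 6.2, 7.1 and 7.2: record all contrast reactions of any grade, later events attributed to contrast (including renal events), and all SAEs regardless of cause.
3. State the start and end of the monitoring period that the DSMC reporting rule uses.
4. If the sponsor prefers not to widen recording, limit any safety statement from the study to immediate reactions. The conflict with section 7.2 would still need to be removed.

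The cost is protocol wording, IRB approval of the amendment, and the recording of SAEs that section 7.2 already requires to be submitted. No new test, visit or analysis is needed.

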### Severity

Adverse events will be graded by a numerical score according to the defined NCI Common Terminology Criteria for Adverse Events (NCI CTCAE) Version 5.0. Adverse events not specifically defined in the NCI CTCAE will be scored on the Adverse Event log according to the general guidelines provided by the NCI CTCAE and as outlined below.

- Grade 1: Mild
- Grade 2: Moderate
- Grade 3: Severe or medically significant but not immediately life threatening
- Grade 4: Life threatening consequences
- Grade 5: Death related to the adverse event

### Serious Adverse Events

ICH Guideline E2A and the UTSW IRB define serious adverse events as those events, occurring at any dose, which meets any of the following criteria:

- Results in death
- Immediately life-threatening
- Results in inpatient hospitalization or prolongation of existing hospitalization
- Results in persistent or significant disability/incapacity
- Results in a congenital anomaly/birth defect
- Based upon appropriate medical judgment, may jeopardize the subject's health and may require medical or surgical intervention to prevent one of the other outcomes listed in this definition.

Note: A “Serious adverse event” is by definition an event that meets **any** of the above criteria. Serious adverse events may or may not be related to the research project. A serious adverse event determination does not require the event to be related to the research. That is, both events completely unrelated to the condition under study and events that are expected in the context of the condition under study may be serious adverse events, independent of relatedness to the study itself. As examples, a car accident requiring  $\geq 24$  hour inpatient admission to the hospital would be a serious adverse event for any research participant; likewise, in a study investigating end-stage cancer care, any hospitalization or death which occurs during the protocol-specified period of monitoring for adverse and serious adverse events would be a serious adverse event, even if the event observed is a primary clinical endpoint of the study.

Pre-planned hospitalizations or elective surgeries are not considered SAEs. Note: If events occur during a pre-planned hospitalization or surgery, that prolong the existing hospitalization, those events should be evaluated and/or reported as SAEs.

 NCI defines hospitalization for expedited AE reporting purposes as an inpatient hospital stay. Hospitalization is used as an indicator of the seriousness of the adverse event and should only be used for situations where the AE truly fits this definition and NOT for hospitalizations associated with less serious events. For example: a hospital visit where a patient is admitted for observation or minor treatment (e.g. hydration) and released in less than 24 hours. Furthermore, hospitalization for pharmacokinetic sampling is not an AE and therefore is not to be reported either as a routine AE or in an expedited report.

7.1.2

### **Unanticipated Problems Involving Risks to Subjects or Others (UPIRSOs):**

The phrase “unanticipated problems involving risks to subjects or others” is found, but not defined in the HHS regulations at 45 CFR 46, and the FDA regulations at 21 CFR 56.108(b)(1) and 21 CFR 312.66. For device studies, part 812 uses the term unanticipated adverse device effect, which is defined in 21 CFR 812.3(s). Guidance from the regulatory agencies considers unanticipated problems to include any incident, experience, or outcome that meets ALL three (3) of the following criteria:

- Unexpected in terms of nature, severity or frequency given (a) the research procedures that are described in the protocol-related documents, such as the IRB-approved research protocol and informed consent document; and (b) the characteristics of the subject population being studied;

**AND**

Study Number – Insert PRMC Assigned SCCC- Protocol Number (found on the PRMC approval letter)

---

- Related or possibly related to participation in the research (possibly related means there is a reasonable possibility that the incident, experience, or outcome may have been caused by the procedures involved in the research);  
**AND**
- Suggests that the research places subjects or others at greater risk of harm (including physical, psychological, economic, or social harm) than was previously known or recognized. Note: According to OHRP, if the adverse event is serious, it would always suggest a greater risk of harm.

Follow-up

All adverse events will be followed up according to good medical practices.

**7.2 Steps to Determine If a Serious Adverse Event Requires Expedited Reporting to the SCCC DSMC and/or HRPP**

Step 1: Identify the type of adverse event using the NCI Common Terminology Criteria for Adverse Events (CTCAE v5).

Step 2: Grade the adverse event using the NCI CTCAE v5.

Step 3: Determine whether the adverse event is related to the protocol therapy.

Attribution categories are as follows:

- Definite – The AE *is clearly related* to the study treatment.
- Probable – The AE *is likely related* to the study treatment.
- Possible – The AE *may be related* to the study treatment.
- Unlikely – The AE *may NOT be related* to the study treatment.
- Unrelated – The AE *is clearly NOT related* to the study treatment.

Note: This includes all events that occur within 30 minutes of the last dose of protocol treatment. Any event that occurs more than 30 minutes after the last dose of treatment and is attributed (possibly, probably, or definitely) to the agent(s) must also be reported as indicated in the sections below.

Step 4: Determine the prior experience of the adverse event. Expected events are those that have been previously identified as resulting from administration of the treatment. An adverse event is considered unexpected, for expedited reporting purposes only, when either the type of event or the severity of the event is not listed in:

**7.2.1**

- the current known adverse events listed in the Agent Information Section of this protocol (if applicable);
- the drug package insert (if applicable);
- the current Investigator's Brochure (if applicable)
- the Study Agent(s)/Therapy(ies) Background and Associated Known Toxicities section of this protocol

**Reporting SAEs and UPIRSOs to the Simmons Comprehensive Cancer Center (SCCC) Data Safety Monitoring Committee (DSMC)**

All SAE/UPIRSOs at all sites, which occur in research subjects on protocols for which the SCCC is the DSMC of record require reporting to the DSMC regardless of whether IRB reporting is required. All SAEs/UPIRSOs occurring during the protocol-specified monitoring period should be submitted to the SCCC DSMC within 5 business days of the PI or delegated study team members awareness of the event(s). In addition, for

Study Number – Insert PRMC Assigned SCCC- Protocol Number (found on the PRMC approval letter)

---

participating centers other than UTSW, local IRB guidance should be followed for local reporting of serious adverse events.

**The UTSW study team is responsible for submitting SAEs/UPIRSOs to the SCCC DSMC Coordinator. Hardcopies or electronic versions of the eIRB Reportable Event report; FDA Form #3500A forms, or other sponsor forms, if applicable; and/or any other supporting documentation available should be submitted to the DSMC Coordinator. The DSMC Coordinator forwards the information onto the DSMC Chairman who determines if immediate action is required. Follow-up eIRB reports, and all subsequent SAE/UPIRSO documentation that is available are also submitted to the DSMC Chair who determines if further action is required. (See *Appendix III of the SCCC DSMC Plan for a template Serious Adverse Event Form which may be utilized when a sponsor form is unavailable and SAE submission to the eIRB is not required*).**

**Reporting Unanticipated Problems Involving Risks to Subjects or Others (UPIRSOs) to the UTSW HRPP/IRB**

UTSW reportable event guidance applies to all research conducted by or on behalf of UT Southwestern, its affiliates, and investigators, sites, or institutions relying on the UT Southwestern IRB. Additional reporting requirements apply for research relying on a non-UT Southwestern IRB.

According to UTSW HRPP/IRB policy, UPIRSOs are incidents, experiences, outcomes, etc. that meet **ALL three (3)** of the following criteria:

1. Unexpected in nature, frequency, or severity (i.e., generally not expected in a subject's underlying condition or not expected as a risk of the study; therefore, not included in the investigator's brochure, protocol, or informed consent document), AND
2. Probably or definitely related to participation in the research, AND
3. Suggests that the research places subjects or others at a greater risk of harm (including physical, psychological, economic, or social harm) than was previously known or recognized. Note: According to OHRP, if the adverse event is serious, it would always suggest a greater risk of harm.

For purposes of this policy, UPIRSOs include unanticipated adverse device effects (UADEs) and death or serious injury related to a humanitarian use device (HUD).

UPIRSOs must be promptly reported to the UTSW IRB within 5 working days of PI awareness.

